6.4 Methods for Evaluation of Measurable Disease

All measurements should be taken and recorded in metric notation using a ruler or calipers. All baseline evaluations should be performed as closely as possible to the beginning of treatment and never more than 4 weeks before the beginning of the treatment.

The same method of assessment and the same technique should be used to characterize each identified and reported lesion at baseline and during follow-up. Imaging-based evaluation is preferred to evaluation by clinical examination when both methods have been used to assess the antitumor effect of a treatment. Clinical lesions will only be considered measurable when they are superficial (e.g., skin nodules and palpable lymph nodes). In the case of skin lesions, documentation by color photography, including a ruler to estimate the size of the lesion, is recommended.

6.4.1 Chest X-ray

Lesions on chest x-ray are acceptable as measurable lesions when they are clearly defined and surrounded by aerated lung. However, CT is preferable.

6.4.2 Conventional CT and MRI

These techniques should be performed with cuts of 10 mm or less in slice thickness contiguously. Spiral CT should be performed using a 5 mm contiguous reconstruction algorithm. This applies to tumors of the chest, abdomen, and pelvis. Head and neck tumors and those of extremities usually require specific protocols.

6.4.3 Cytology, Histology

The cytological confirmation of the neoplastic origin of any effusion that appears or worsens during treatment when the measurable tumor has met criteria for response or stable disease is or stable disease (an effusion may be a side effect of the treatment) and progressive disease.

6.5 Primary Endpoint

Rate of progression-free survival at 3 months. Time from enrollment to progression, with progression defined as changes in RECIST 1.1 defined imaging, progression in non-target lesions as defined by RECIST 1.1, unequivocal clinical deterioration, or death from any cause. Cohort 1 and 2 analyzed separately.

6.6 Secondary Endpoints (cohorts 1 and 2 analyzed separately).

- The presence of response (ORR-CR+PR) per RECIST version 1.1
- The presence of clinical benefit (CR+PR+SD) per RECIST version 1.1
- The endpoint is to determine OS and PFS for subjects in Cohort 1 and 2 (separately) treated with combination cabozantinib and temozolomide.
- The presence of all toxicities outlined in NCI CTCAE 5.0 from time of first treatment.

7.0 REPORTING OF ADVERSE EVENTS UNANTICIPATED PROBLEMS & OTHER EVENTS OF INTEREST

The research team is responsible for classifying AEs and UPs as defined in the relevant regulations and reporting to all applicable parties, including but not limited to the COH IRB, DSMC, Food and Drug Administration (FDA), National Institutes of Health (NIH) and other collaborators, e.g., pharmaceutical companies. The research team is responsible for the continued monitoring and tracking of all AEs in order to ensure non-reportable events are reviewed and monitored and do not rise to a reporting level.

7.1 Assessment of Adverse events

The site Investigator will be responsible for determining the event name, and assessing the severity (i.e., grade), expectedness, and attribution of all adverse events as applicable per the [City of Hope Clinical Research Adverse Event and Unanticipated Problem policy \(available from the DCC\)](#). Adverse events will be characterized using the descriptions and grading scales found in **NCI CTCAE v5.0**.

A copy of the scale can be found at:

https://ctep.cancer.gov/protocoldevelopment/electronic_applications/ctc.htm.

Per the CTCAE 5.0 an Adverse Event is any unfavorable and unintended sign (including an abnormal laboratory finding), symptom, or disease temporally associated with the use of a medical treatment or procedure that may or may not be considered related to the medical treatment or procedure. An AE is a term that is a unique representation of a specific event used for medical documentation and scientific analyses.

The following definitions will be used to determine the causality (attribution) of the event to the study agent or study procedure.

- **Unrelated** – The event is clearly NOT related to study treatment, and is clearly related to other factors such as the participant’s clinical state, other therapeutic interventions, or concomitant medications administered to the participant.
- **Unlikely** – The event is unlikely related to the study treatment, and is most likely related to other factors such as the participant’s clinical state, other therapeutic interventions, or concomitant drugs.
- **Possible** – The event may be related to study treatment, as it follows a reasonable temporal sequence from the time of drug administration, but could have been produced by other factors such as the participant’s clinical state, other therapeutic interventions, or concomitant drugs.
- **Probable** – The event is most likely related to the study treatment, as it follows a reasonable temporal sequence from the time of drug administration and a known response pattern to the study drug, and is unlikely related to the participant’s clinical state, other therapeutic interventions, or concomitant drugs.
- **Definite** – The event is clearly related to the study treatment, as it follows a reasonable temporal sequence from the time of drug administration and a known response pattern to the study drug, and is not reasonably explained by other factors such as the participant’s condition, therapeutic interventions, or concomitant drugs.

7.2 Adverse Events of Special Interest (AESI)

There are no Adverse Events of Special Interest for this study.

7.3 Routine AE Collection and Reporting Guidelines

AEs will be collected from the signing of informed consent until ending study participation. Routine AE reporting will occur via data entry into the study eCRF. AEs will be monitored by the Protocol Management Team (PMT). AEs reported through expedited processes (e.g., reported to the IRB, FDA, etc.) must also be reported in routine study data submissions.

AEs recorded in the eCRF include:

- Any Grade 1-5 AE during Cycle 1
- Highest grade AE in subsequent cycles
- All SAEs

7.4 Expedited Reporting

Table 0-11 indicates what events must be reported expeditiously. Adverse events that meet the criteria of serious OR are unanticipated problems will be reported according to the approved [City of Hope Clinical Research Adverse Event and Unanticipated Problem policy](#). Reporting of SAEs will begin on or after Cycle 1 Day 1 and must be followed until the event is resolved, stabilized, or determined to be irreversible by the investigator. Follow-up SAE reports must be submitted for all events that require expedited reporting when the status of the event changes and until the resolution or stabilization of the event.

Table 0-11: Criteria for Expedited Reporting

Time point	What to report
From signing of the consent to study completion	
 • All UPs
For the time period beginning at treatment through 30 days following cessation of treatment	
 • All SAEs regardless of relationship to protocol therapy • All UPs and AEs that meet the definition of a UP • AESIs (Section 7.2)

From Day 1 of protocol therapy up to 120 days post-last dose of study therapy	
 • Pregnancies and lactation
Post Safety Follow-Up to removal from study	
 • All SAEs that are considered possibly, probably or definitely related to cabozantinib or temozolomide.

NOTE: All events reported expeditiously require follow-up reporting until the event is resolved, stabilized, or determined to be irreversible by the investigator.
 
The DCC should be consulted prior to ending the follow-up of events that have stabilized.
	

Expedited reporting guidelines (COH only):

Serious Adverse Events that require expedited reporting and unanticipated problems will be reported according to the approved City of Hope Clinical Research Adverse Event and Unanticipated Problem policy. This includes all SAEs and UPs that meet COH DSMC/IRB expedited reporting criteria that

occurred at COH and non-COH sites. For non-COH sites, the DCC will be responsible for reporting.

Expedited reporting guidelines (Non-COH Sites):

All events that meet the criteria specified in Table 0-11 will be reported to the Data Coordinating Center (DCC) and PI within 24 hours of notification that the event met the expedited reporting criteria.

Procedure for reporting SAEs/UPs to the COH DCC:

1. Sites are to report to their local IRB per their site's specific institutional and IRB guidelines. As soon as possible, non-COH sites will provide to the COH DCC copies of the IRB submission and corresponding IRB response.
2. Document/describe the SAE/UP on each of the following:
 - a. MedWatch 3500A or local IRB submission document*

MedWatch 3500A: Downloadable form at
<http://www.fda.gov/medwatch/getforms.htm>

*The local IRB submission document may be used if the document template is approved by the DCC.
 - b. Expedited Reporting Coversheet: A modifiable Microsoft Word document is available from the DCC. An electronic signature on the document will be accepted.
3. Scan and email above documents to the Study PI ([contact]) and [contact] with the subject title as "COH IRB 20664 SAE". If available, sites may include the local IRB submission for this event in the submission.
4. If an email receipt from DCC personnel is not received within one working day, please email [contact].

7.5 Reporting to the FDA

The study PI (or designee) will be responsible for contacting the Office of IND Development and Regulatory Affairs (OIDRA) at COH to ensure prompt reporting

of safety reports to the FDA. OIDRA will assist the PI with the preparation of the report and submit the report to the FDA in accordance with the approved [City of Hope Clinical Research Adverse Event and Unanticipated Problem policy](#).

Serious Adverse Events meeting the requirements for expedited reporting to the Food and Drug Administration (FDA), as defined in [21 CFR 312.32](#), will be reported as an IND safety report using the [MedWatch Form FDA 3500A for Mandatory Reporting](#).

The criteria that require reporting using the MedWatch 3500A are:

- Any unexpected fatal or life threatening adverse experience associated with use of the drug must be reported to the FDA **no later than 7 calendar days** after initial receipt of the information [[21 CFR 312.32\(c\)\(2\)](#)]
- Any adverse experience associated with use of the drug that is both serious and unexpected must be submitted **no later than 15 calendar days** after initial receipt of the information [[21 CFR 312.32\(c\)\(1\)](#)]
- Any follow-up information to a study report shall be reported **as soon as** the relevant information becomes available. [[21 CFR 312.32\(d\)\(3\)](#)]

In addition, on behalf of the study PI, OIDRA will submit annually within 60 days of the anniversary of the date the IND went into effect, an annual report to the FDA which is to include a narrative summary and analysis of the information of all FDA reports within the reporting interval, a summary report of adverse drug experiences, and history of actions taken since the last report because of adverse drug experiences.

7.6 Reporting to Exelixis

7.6.1 SAE Reporting to Exelixis

All SAEs, regardless of attribution, and all pregnancy/lactation reports regardless of outcome must be sent to Exelixis within one (1) business day of the PI's knowledge of the event. The reports must be sent to

[contact] or [contact]. Please ensure to include the Exelixis study number for the protocol - IST87 clearly on the Medwatch 3500A or local IRB reporting form.

The PI will perform adequate due diligence with regard to obtaining follow-up information on incomplete reports. All follow-up information must be sent to Exelixis within one (1) business day of the PI's receipt of the new information. Upon Exelixis request, the PI will query for follow-up information.

The Investigator will assess the expectedness of each related SAE. The current cabozantinib Reference Safety Information will be used as the reference document for assessing the expectedness of the event with regard to cabozantinib. All serious unexpected adverse drug reactions (unexpected related SAEs) must be reported to all appropriate regulatory authorities and Ethics Committees by the investigator as required by 21 CFR 312.32 or by Directive 2011/20/EC:

- These reports are to be filed utilizing a Medwatch 3500A or local IRB reporting Form;
- Exelixis reserves the right to upgrade the Investigator assessment of an SAE based on Exelixis assessment.
- Institutions and PIs shall promptly provide all information requested by Exelixis regarding all adverse events occurring during the conduct of the study.

7.6.2 Regulatory Reporting to Exelixis

- The PI is responsible for complying with all regulatory authority reporting requirements for the study that are applicable to the sponsor of a clinical trial. The PI shall provide a copy of all responses to regulatory agency requests, periodic reports, and final study reports to Exelixis within one (1) business day of the submission.
- Exelixis will provide relevant product safety updates and notifications, as necessary. In the case of multi-center studies, it is

the responsibility of the sponsoring PI/Institution to disseminate these updates to participating PIs.

7.7 Reporting to Participating Investigators

The study PI (or designee) will report all reportable serious adverse events to participating investigators on a MedWatch 3500A form within 30 calendar days of notification of the event. A cover letter will indicate the protocol title, the IND# and whether the FDA was informed (if applicable), whether or not a protocol and/or consent form change is required, and for non-COH sites, a statement that the report should be submitted to their local IRB for review if applicable per local IRB policy.

The study PI will also forward to participating sites all IND safety reports received from Exelixis within 30 days of notification, indicating whether a consent form or protocol change is required.

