Drug interaction and increased toxicity is not anticipated; however, there is limited clinical experience with the combination of cabozantinib and temozolomide. To exclude prohibitive toxicity, up to 14 subjects will be treated with combined therapy as outlined above. If a subject goes off treatment before completing a 4 week observation period of safety run-in for reasons other than toxicity, then that subject should be replaced. Accrual will be interrupted after the initial 14 subjects have been enrolled. All subjects in the run-in cohort will be observed for at least 2 weeks after completion of Cycle 1 for toxicities.

Table 0-1: Dose Reductions of Cabozantinib

Assigned Dose	First Dose Level Reduction	Second Dose Level Reduction
40-mg cabozantinib oral qd	20-mg cabozantinib oral qd	No dose reduction permitted
qd, once daily Cabozantinib will be discontinued if a qd dose of 20-mg cabozantinib (minimum dose) is not tolerated		

Table 0-2: Dose Modifications of Cabozantinib for Treatment-Related Averse Events

CTCAE v.5.0 Grade	Recommended Guidelines for Management ^a
Grade 1 AEs	
 Add supportive care as indicated. Continue cabozantinib treatment at the current dose level if AE is manageable and tolerable.

Grade 2 AEs which are tolerable and are easily managed	
 Continue cabozantinib treatment at the current dose level with supportive care.
Grade 2 AEs which are intolerable and cannot be adequately managed	
 At the discretion of the investigator, cabozantinib may be dose reduced or interrupted. 
*Note: It is recommended that dose holds be as brief as possible.

Grade 3 AEs (except clinically non-relevant laboratory abnormalities)	
 Cabozantinib should be interrupted unless the toxicity can be easily managed with a dose reduction and optimal medical care. 
*Note: It is recommended that dose holds be as brief as possible.

Grade 4 AEs (except clinically non-relevant laboratory abnormalities)	
 Subjects should have cabozantinib interrupted immediately. Discontinue cabozantinib unless the following criteria are met: 
 Subject is deriving clear clinical benefit as determined by the investigator Toxicity can be managed with a dose reduction following recovery to Grade 1 (or baseline) and optimal medical care

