- d. Thyroid function tests (TSH, FT3, FT4) are performed during the screening period and then every 8 weeks (\pm 5 days). TSH is mandatory, FT3/FT4 are only required to be performed if TSH level is abnormal. Screening test should be done within 28 days of Cycle 1, Day 1.
- e. Pregnancy test: urine or serum at screening and on Day 1 of each cycle (\pm 5 days) for women of child-bearing potential.
- f. Urine protein/urine creatinine will be assessed during screening and **every 2 cycles** (\pm 5 days of D1 of the cycle) until the end of treatment. Screening UPCR should be done within 14 days of Cycle 1, Day 1 in which case Cycle 1, Day 1 assessment may be skipped.
- g. End of treatment visit will be completed within 30 days of the last dose of study drugs. Subjects with PD at end of treatment will be followed every 6 months for 2 years (or until death) for survival (from the last day of treatment). Subjects without PD at the end of treatment will be followed every 6 months for 5 year (or until death) for survival and progression (from the last day of treatment).
- h. The QOL questionnaires (EORTC QLQ-C30 and EuroQoL EQ-5D-3L) should be completed during screening, on Day 1 of every cycle prior to the study treatment administration, and at the end of treatment.
- i. Blood samples for mandatory correlative study will be collected at Cycle 1 Day1 prior to starting the treatment, and at C2D15, C4D1, and at the end of treatment (EOT) visit (\pm 5 days).
- j. Day 1 of each cycle should be every 28 days. In the event that this day falls on a holiday or other such event, study team should use \pm 5 days window to complete pre-treatment procedures, and dispense protocol agents to subjects with drug diaries and instructions to commence treatment on Day 1. Any missed doses will not be made up and should be skipped to maintain a 28-day cycle. Collection of drug diaries and drug accountability will be completed for the previous cycle on Day 1 of the following cycle.
- k. Screening PT/INR and PTT should be within 14 days of registration.
- l. Subjects with prior Next Generation Sequencing (NGS) reports completed on their tumor specimen will have this data collected.

*Once on treatment, if the subject is unable to have a study assessment taken within the defined time window due to an event outside of his or her control (e.g., clinic closure, personal emergency, inclement weather, vacation), the assessment should be performed as close as possible to the required schedule.

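### Section 7.7 gives up to 30 days to tell participating investigators of every reportable SAE, with no shorter limit for events that must reach the FDA in 7 or 15 days, and 30 days is longer than one 28-day cycle

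*Combined protocol and SAP*

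**What the plan says.** Section 7.7 sets two outbound limits from the study PI to the other sites. Reportable serious adverse events go "to participating investigators on a MedWatch 3500A form within 30 calendar days of notification of the event". The PI also forwards "all IND safety reports received from Exelixis within 30 days of notification". The cover letter for the first states whether the protocol or consent form must change; the forwarded Exelixis reports carry the same indication. Neither limit varies with the severity or expectedness of the event.

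Section 7.5 grades its deadlines. The shortest is a 7-day limit, in calendar days from when the information first arrives: "Any unexpected fatal or life threatening adverse experience associated with use of the drug must be reported to the FDA". An event that is both serious and unexpected is due "no later than 15 calendar days". The form is the same MedWatch 3500A that Section 7.7 names.

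The inbound limits are short. Under Section 7.4, non-COH sites report qualifying events to the Data Coordinating Center and PI within 24 hours. Under Section 7.6.1, Exelixis receives every SAE within one business day. Section 7.6.2 makes the sponsoring PI or institution responsible for passing Exelixis safety updates to participating PIs but gives no time limit.

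On the treatment calendar, footnote j of Section 5.0 states: "Day 1 of each cycle should be every 28 days". Section 4.2 gives temozolomide on Days 1-5 and raises it from 150 to 200 mg/m² from Cycle 2 if neutrophil and platelet thresholds are met. Section 4.4 says that "there is limited clinical experience with the combination of cabozantinib and temozolomide".

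**The concern.** Investigators at the participating sites make the interruption, reduction and escalation decisions for their own subjects. For a serious unexpected event at another site, the coordinating center, the drug supplier and the FDA all have stated limits of 15 days or less. The investigators treating subjects elsewhere have a stated limit of 30 days.

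That matters more here because the protocol itself describes experience with the combination as limited, and Section 1.3 says that the Cycle 1 temozolomide dose was changed because of observed toxicity. An investigator who does not yet know of a fatal unexpected event can start a subject's next course, or the planned Cycle 2 increase, without that information. A required consent or protocol change announced in the same letter can be equally late.

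**Working it through.** No sample size, power or alpha figure is involved. The check compares the protocol's own deadlines with each other and with the cycle length.

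**Inputs**
- Notice to participating investigators: 30 calendar days (Section 7.7).
- Forwarding of Exelixis IND safety reports: 30 days (Section 7.7).
- FDA, unexpected fatal or life-threatening: 7 calendar days (Section 7.5).
- FDA, serious and unexpected: 15 calendar days (Section 7.5).
- Cycle length: 28 days (Sections 4.2, 4.3 and 5.0).
- Temozolomide: 150 mg/m² in Cycle 1, then 200 mg/m² if ANC is at least 1.5 × 10⁹/L and platelets are at least 100 × 10⁹/L (Section 4.2).
- Safety lead-in: 14 subjects; planned total 72 (Study Summary).

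**Gap to the FDA deadline**, assuming that both clocks start on the same day:
- Unexpected fatal or life-threatening: 30 − 7 = 23 days.
- Other serious unexpected: 30 − 15 = 15 days.

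**Gap to the cycle length**: 30 − 28 = 2 days longer than one cycle.

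**New cycles started before notice is due.** Suppose the PI is notified at the end of any one of the 28 cycle days of an on-schedule subject at another site, each day equally likely. The share of subjects who reach a new Day 1 within W days is min(W, 28)/28.

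| Limit W | Share reaching at least one new Day 1 |
|---|---|
| 7 days | 7/28 = 25% |
| 15 days | 15/28 = 54% |
| 30 days | 28/28 = 100% |

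At 30 days the minimum is one new Day 1 and the maximum two. Two of the 28 starting positions (2/28 = 7%) give two, and the mean is 30/28 = 1.07. The 100% does not depend on the equal-likelihood assumption, but it does require an undelayed schedule and use of the full window.

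**Escalation.** For a subject in Cycle 1, the next Day 1 is the planned increase of (200 − 150)/150 = one third, conditional on counts.

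**Do other provisions close the gap?**
- *Grade 5 hold (Study Summary, Section 10.3).* It applies during the 14-subject lead-in, so up to 72 − 14 = 58 planned subjects enroll after it. It holds accrual. It does not require notice to sites and does not address subjects already on treatment.
- *Protocol Management Team (Section 14.3).* Collaborating investigators are members and SAEs are on its agenda, but meetings are only recommended and no interval is given.
- *DSMC (Section 14.6).* It raises safety questions with the Protocol Management Team. No route to sites is stated.

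No other section supplied sets a shorter outbound limit.

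**The case against.** **A ceiling is not an outcome.** Thirty days is the latest date, and the PI may notify much sooner. A reader might infer that other sites will start another course before hearing of a fatal event. The documents support only that they can: it is certain only if the full window is used and the subject is on schedule. This limit stands.

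**Sources outside the file.** Sections 7.1, 7.4 and 7.5 refer to a City of Hope adverse event policy, and Sections 7.5, 7.6.1 and 15.2 cite 21 CFR 312.32 or Part 312. Neither text is available here, and either might impose a faster duty. The supportable statement is that Section 7.7 contains no faster track, not that none applies. A site reading the protocol would still see 30 days.

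**Not every other recipient has a short clock.** A reader might infer that the treating investigators are the only party without one. DSMC and IRB timing is left to that policy or to local guidelines, without a number of days. Only the coordinating center and PI, Exelixis and the FDA have explicit short limits.

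**Enrollment.** A reader might multiply the accrual rate of about 3 per month by the 30-day window and conclude that about 3 more subjects would be enrolled uninformed. The documents do not support this. The rate in Section 10.2 is study-wide and includes the lead site. Under Sections 11.3 and 11.4 the coordinating center controls slots and confirms every registration, and it hears of non-COH events within 24 hours. The gap mainly concerns subjects already on treatment.

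**No contradiction.** Sections 7.5 and 7.7 address different recipients and can both be followed. This is correct: the point is a weak design choice, not an inconsistency.

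**Other review steps.** Investigators review all grade 3 and 4 toxicities after the first 14 subjects complete Cycle 1, and Section 4.4 interrupts accrual then. These are one-time steps and do not give prompt notice of a particular event.

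**Conclusion.** The concern holds as a weakness in a stated rule. Section 7.7 permits notice of an unexpected fatal or life-threatening event to fall due up to 23 days after the FDA deadline, and of another serious unexpected event up to 15 days after it. Since the limit is 2 days longer than a cycle, every on-schedule subject at another site can reach at least one new temozolomide course before notice is due, and a subject in Cycle 1 can reach the escalated course if counts permit. The same 30 days applies to Exelixis IND safety reports.

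These figures assume that the FDA and site clocks start together, that the full 30 days is used, and that cycles are not delayed. They describe what the wording allows and do not predict what would happen. The change should be made: it concerns subject safety, and the existing hold and committee provisions do not cover subjects on treatment at other sites.

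**What to change.** Amend Section 7.7 as follows:
- Reports of events meeting the Section 7.5 criteria go to all participating investigators together with the FDA submission, and no later than the same 7- or 15-calendar-day limit.
- The same limits, counted from receipt, apply to IND safety reports received from Exelixis.
- All sites receive prompt notice of any accrual hold and of the event that triggered it. The documents give no basis for a specific number of hours or for same-day notice, so the sponsor should set the interval.
- The 30-day limit stays for other reportable SAEs only.

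This changes communication timing and no dose or treatment rule. For FDA-reportable events the MedWatch 3500A already exists when the submission is made, so the cost is a wording amendment and slightly earlier e-mailing by the coordinating center.
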